6.1. Purpose and Study Arms

This pivotal investigational study is designed to evaluate the safety and efficacy of a skin tag removal (STR) study device. This is a non-significant risk interventional clinical study that will be conducted by a Clinical Research Organization (CRO) with a licensed dermatologist(s) to serve as Principal Investigator. There are two arms of the study that are only differentiated by the type of STR study device used; arm 1 will be conducted using the manual version, and arm 2 will use the automatic version.

After consultation with the FDA, the Sponsor has modified the original protocol to include the following changes:

- Exclusion of all skin tags located around the eye, on the eyelid, or the groin area (6.2.1)
- Clarification of covered medical expenses while enrolled in the study (6.2.4)
- Protocol includes updated exclusion conditions (excluding those with known hypertrophic scarring or keloid scarring)
- Protocol includes the addition of an electronic daily diary for all participants
- A study was conducted to power the investigation for biostatistical relevance properly (please see the report in the Reference section). The conditions for power analysis were:
 - The primary endpoint is the removal of the skin tag (effectiveness)
 - The observed percentage of successful removal is 60%; i.e. 60% of the skin tags treated are expected to be successfully removed with use of the device
 - A 95% Confidence Interval (CI) was used to determine the number of subjects necessary for participation

Determination: if a successful clinical trial is established at 60% of treated skin tags removed, a study powered with 200 treated tags will have a 95% confidence interval of 5.5%

The power analysis determined that the sponsor should enroll enough subjects to treat a total of 200 skin tags. Typically, patients seeking skin tag removal have from 1 to 5 tags that could be treated for removal, however, for this study, only a maximum of 2 tags per person will be treated. Therefore, the number of tags for intention to treat (ITT) in each arm is 100 for a study total of 200 tags. This approach will ensure that the study has been powered to a 95% confidence interval of 5.5%.

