Therefore, the total intention to treat (ITT) is 200 skin tags for arms 1 and 2 combined. If the study is completed with subjects only having one skin tag treated, then the study would need to recruit 200 subjects. If each subject had two skin tags treated, only 100 subjects would need to be recruited. It is anticipated that between 100 and 200 subjects will be required to treat a total of 200 skin tags.

The figures below depict how the total subject pool would be divided into the two arms under both versions of the protocol, where "N" is the number of subjects:

Under Protocol Version 1: Figure 1

[figure not shown]

Figure 1: Breakdown of subjects into each arm and size of band used to be stratified as equally as possible in the targeting of ~200 treated skin tags.

[figure not shown]

Figure 2: Breakdown of subjects into each arm to be stratified as equally as possible in the targeting of ~200 treated skin tags.

Once enrolled in the study, the Investigator will assign an STR version for use (manual/ automatic . Only the micro-sized band will be used in this version of the protocol, and only skin tags measuring 4–6mm at the base will be eligible for treatment. The Investigator will also review the subject's skin tags and agree with the subject on the body location and skin tag(s) that will be treated (see exclusion criteria) . The Investigator will also verify that the skin tag does not present a morphology representing implications of cancerous tissue. After signing informed consent and reviewing device lab,eling as well as determining eligibility , the subject will then have the band(s) placed on the skin tag(s) by the healthcare professional.

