6.2.6. Clinical Endpoints

Primary clinical endpoints and data collected are defined as follows:

Primary Outcome	Time Frame	Description and Data Collected
Successful removal of acrochordons using the STR device	Visit 1: subject screening and band placement (in-clinic)	 Obtain subject's informed consent Study team member to verify inclusion/exclusion criteria Identification of skin tag(s) to be used in study, including size (micro or standard) and location Documentation of body location and number of tags Investigator to stratify subject into either manual or automatic device arm Placement of band(s) by Investigator Placement of bandage(s) by investigator Subject to read after-care instructions & review any questions with study team Subject will receive clinical eDiary instructions comprising of device use, comprehension, and adverse events and later complete Day 1 entry Subject will upload a photo of the banded skin tag(s) in clinic

	 during Visit 1, which will be reviewed by the site staff Study team member to remind subject that an in-clinic visit is always available upon request and to call with any questions or concerns Study team member to remind subject to schedule an in-clinic rebanding visit at their earliest convenience in the event of premature band detachment
Visit 2 (virtual)	At Visit 2, the subject is to complete a remote visit where the following activities are performed: • Subject and study team member will review the photos and verify eDiary compliance for all days up to Visit 2 and also identify any signs of infection, irritation, or other adverse events • Study team member to record general observations of tag(s) treated, flagging any concerns to Investigator • Study team to review any instances of premature band detachment, and to remind participant to schedule a rebanding visit if not already completed • Subject to continue filling out eDiary through Day 2 oregardless if skin tag(s) remain(s) • Study team member to review after care instructions that are to be followed through Visit 4 • Study team member to remind subject that an in-person visit is always available upon request and to call with any questions or concerns

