6.2.6.1. Reported Post Study Data

Case Report Forms will be used by the CRO to collect and organize data. All data collected during the investigational study will be compiled by the CRO and securely stored by the Sponsor. Data collected will be captured and archived using a per-protocol approach.

The following table provides a list of the reported primary outcomes, as evidenced by the study. Data subgroup analysis following the completion of the study and performance data analysis reported by:

- Age (22-50 vs. 51+)
- Sex assigned at birth (M/F)
- Band size (micro vs. standard)
- Band detachment events, including duration of detachment
- Body location of band placement
- Mechanism of device used (automatic vs. manual)

Data Collected	Description
Proper band placement	Source: Visit 1, Investigator Records STR study device bands will be placed on up to two (2) skin tag(s) by the Investigator. Source: eDiary Participant will upload a photo(s) of the banded skin tag(s) in the eDiary at the Visit 1 in-clinic visit.

Efficacy of skin tag removal	Source: Days 2-2 O, Case Report Forms and Subject eDiary The total number of skin tags treated and those successfully removed by use of the STR study device will be compiled and reported. In all cases, the removal rate will be categorized by skin tag size (micro or standard) and body location as well as subject demographics
Safety and Potential Health Impacts	Source: Case Report Forms and Subject eDiary There are not any serious adverse effects anticipated with this study potential non-serious side effects during the use of the STR study device are as follows and will be collected: Irritation Tenderness Pigment change Scarring Less common but potential side effects that need to be collected and addressed are: Infection Redness or swelling at the base of tag Bleeding Pain Delayed healing (greater than 14 days after tag falling off/removal) Hypertrophic or Keloid scarring Other (as defined/described in the eDiary manual) General use comments by the subjects, including photos depicting the progression of the skin tag(s) treatment and after the tag has fallen of Only adverse events associated with the device will be recorded and documented as Adverse Device Effects (ADEs).

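### The Investigator chooses the manual or automatic arm with no random or concealed allocation, so the per-arm and automatic-versus-manual removal rates are open to selection bias

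*Protocol*

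**What the plan says.** Section 6.1 defines "two arms of the study that are only differentiated by the type of STR study device used": manual in arm 1 and automatic in arm 2. It sets the size by tags: "the number of tags for intention to treat (ITT) in each arm is 100 for a study total of 200 tags". The arm tables in the same section give each arm its own goal of 60% of treated tags removed.

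Two places deal with allocation:

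- Section 6.2.1: once a subject is enrolled, "the Investigator will assign an STR version for use".
- Section 6.2.6, Visit 1: "Investigator to stratify subject into either manual or automatic device arm".

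Two places deal with the choice of tags:

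- Section 6.2.1, directly after the device assignment: "The Investigator will also review the subject's skin tags and agree with the subject on the body location" and the tags to be treated.
- Section 6.2.6, Visit 1, listed before the arm step: "Identification of skin tag(s) to be used in study, including size (micro or standard) and location".

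The balancing aims are arms of about equal size (6.2.1, figure captions) and a spread of body sites, managed by the Principal Investigator (6.1). The second concerns the study as a whole, not balance between arms. Section 6.2.6.1 lists, among the subgroup results to be reported, "Mechanism of device used (automatic vs. manual").

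**The concern.** The person who allocates the applicator has examined the tags and helps choose them. Section 2.1 gives a reason why visible features could predict the outcome: larger, broad-based lesions are said to resist compression at the base more. Section 6.2.2 adds discretion over size, since the Investigator may round a tag above 6 mm down into the eligible range. If the Investigator tends, even without intent, to use one applicator for certain sites or shapes, the arms will hold different tags.

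At stake are two planned outputs: whether each applicator reaches its 60% goal, and the comparison of automatic with manual that a reader will draw from the results by mechanism. A difference there could reflect which tags went to which applicator. A statistical analysis plan cannot repair this fully, because the protocol itself fixes the allocation rule and enrolment carries it out.

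**Working it through.** **1. The plan's own figure.** The plan gives no precision figure for the arms or their difference. Its only sizing statement is pooled: 200 tags at 60% removal with a 95% confidence interval of 5.5% (section 6.1). The normal-approximation half-width is 1.96 × √(0.6 × 0.4 / 200) = 0.068, or 6.8 points. At 80%, the rate in protocol version 1, it is 1.96 × √(0.8 × 0.2 / 200) = 0.055. So 5.5% is not reproduced at 60%. That is a separate matter and does not bear on allocation.

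**2. Does the order of the two choices matter?** Section 6.2.1 mentions the device first, but links the tag review to it only with the word also, and the same paragraph comes to consent and eligibility last. It is not a clear timeline. The Visit 1 list in 6.2.6 puts tag identification before the arm step, and eligibility under 6.2.2 already requires a qualifying tag. The order is not settled. If the device came first, tags could be picked to suit it; if the tags came first, the device could be matched to them. Bias is possible either way.

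**3. Possible size.** The protocol gives no removal rates by tag type, so these inputs are assumptions. Let removal be pE for easy tags and pH for hard tags, the same with both applicators, and let the share of easy tags be sA in one arm and sB in the other.

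Expected rate in an arm = s × pE + (1 − s) × pH, so the false difference = (sA − sB) × (pE − pH).

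With pE = 0.70 and pH = 0.50:

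- 60% v 40% easy: 0.6 × 0.7 + 0.4 × 0.5 = 0.62 and 0.4 × 0.7 + 0.6 × 0.5 = 0.58; false difference 4 points.
- 70% v 30% easy: 0.49 + 0.15 = 0.64 and 0.21 + 0.35 = 0.56; false difference 8 points.
- 80% v 20% easy: 0.56 + 0.10 = 0.66 and 0.14 + 0.40 = 0.54; false difference 12 points.

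In each case the expected rates fall on opposite sides of 60%, while the pooled rate with equal arms stays at 60%.

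Over the same three mixes, 65% and 55% removal gives false differences of 2, 4 and 6 points, and 80% and 40% gives 8, 16 and 24.

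**4. Against random error.** With 100 tags per arm at 60%, treated as independent, the 95% half-width is 1.96 × √(0.24 / 100) = 9.6 points per arm and 1.96 × √(2 × 0.24 / 100) = 13.6 points for the difference. If a reader formed that interval, the chance that it excludes zero with no true device effect would be 9%, 21% and 42% for the 4-, 8- and 12-point cases, against a nominal 5%.

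**The case against.** The strongest reply is that no comparison is planned. The aim in section 2.2 is the proportion of tags removed within 20 days and the safety outcomes; the sizing is a single-proportion interval; and no between-arm hypothesis, test or margin is stated. Mechanism is one reporting subgroup beside age and sex, which are not randomised either. Section 3.1 says that all versions of the device work in the same way. This stands, and it limits the point to the per-arm and by-mechanism results.

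The illustrated rates and mixes are assumptions, and the 4- to 12-point differences lie within the 13.6-point half-width. Random error alone could also put the two arms on opposite sides of 60%. That stands too. But random error is shown by a confidence interval, and selection bias is not.

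Three stronger readings are tempting and are not supported:

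- A reader of 6.2.1 alone might infer that tags are picked after the arm is known. The Visit 1 list has the reverse order, and 6.2.1 fixes none.
- A reader might take "There are two arms of the study that are only differentiated by the type of STR study device used" as a claim that the arms hold comparable tags, which the allocation rule would then contradict. It more naturally says how the arms are defined.
- A reader might infer from the 13.6-point half-width that later adjustment is of little use. The half-width measures random error and does not show that. Tag size and location are recorded, so results can be shown by both, although base shape is not a listed item.

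**Conclusion.** The point holds with limited scope. The Investigator chooses the arm and, with the subject, the tags, and no random or concealed method is stated. The results of each arm against 60% and the results by mechanism are therefore open to selection bias in either order of choice. With 70% and 50% removal assumed and no device effect, the false difference is 4 to 12 points over the mixes shown; over the wider range of assumed rates it is 2 to 24 points. These figures show what could happen, not what has happened.

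A reader might conclude that the trial cannot meet its purpose. The protocol does not support that: its stated aim is met by the pooled rate, which does not rest on how tags are divided between the applicators. This is a low-cost improvement to a stated rule, not a defect in the pooled result.

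**What to change.** For remaining enrolment:

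- Confirm eligibility and record the tag or tags to be treated, with size and location, before the device is known. The Visit 1 list already suggests this order; section 6.2.1 should be brought into line with it.
- Then take the device from a concealed, computer-generated 1:1 permuted-block list by subject. Both tags of a subject stay in the same arm, as 6.2.1 already requires.
- Put this rule in place of "the Investigator will assign an STR version for use" in 6.2.1 and "Investigator to stratify subject into either manual or automatic device arm" in 6.2.6.

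For reporting, label any per-arm or automatic-versus-manual result that includes subjects enrolled before the change as descriptive and non-randomised, and show it by tag size and body location.

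The cost is a short amendment and an allocation list. The number of tags does not change, and section 6.2.3 already has the Investigator trained on both applicators. The downsides are that the Investigator loses discretion over the device, that earlier subjects stay non-randomised, and that tag counts per arm may not be exactly equal, because subjects contribute one or two tags. Random allocation does not improve precision: the difference would still have a half-width of about 13.6 points.

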6.2.2. Inclusion/Exclusion Criteria

Enrollment in the study will be limited to participants who meet all of the following inclusion criteria and none of the exclusion criteria:

Inclusion Criteria

- 1. Adults at least 22 years of age.
- 2. Must be able to understand, speak, and read English sufficiently for completion of the trial.
- 3. Subject has at least one skin tag meeting ALL of the following requirements:
 - a. no previous attempts to remove the skin tag(s) of investigation, including skin tags that were treated in a previous version of this protocol
 - b. measuring between 4 mm and ~6mm at the base. S kin tags measuring larger than 6mm can be rounded down based on investigator's discretion.
 - c. not located around the eye, on the eyelid, or in the groin area
 - d. if treating two tags, only one may be located in axilla
 - e. free of any active skin infection & area to treat tag has no severe eczema
 - f. located in an area where participant can take a self-taken photo
 - g. does not, in the opinion of the Investigator, require an evaluation by pathology at the time of screening
- 4. Subject has access to the internet via smartphone to complete the eDiary.

Exclusion Criteria

- Significant medical condition or other circumstance which, in the opinion of the Investigator, would preclude compliance with the protocol, adequate cooperation in the trial or providing informed consent, or may prevent the subject from safely participating in the trial
- 2. Any prior history of skin-related cancer
- 3. Subject states that they are currently pregnant or intending to become pregnant during the course of the study
- 4. Has an allergy to latex
- 5. Current diagnosis of a bleeding disorder included but not limited to Hemophilia or Von Willebrand disease
- 6. Currently being treated with blood thinners (use of 81 mg of Aspirin is not exclusionary)
- 7. Currently being treated with topical steroids at site of skin tag of interest or oral steroids
- 8. Currently immunocompromised by conditions such as diabetes (either Types 1 or 2, regardless of level of control) or receiving immunosuppressant therapy
- 9. Current MRSA infection
- 10. Diagnosis or any history of keloid or hypertrophic scarring

 Current or recent participation within the last 30 days in another interventional clinical trial

6.2.3. Study Procedures

Demographics

Participants will provide demographic information at the baseline visit. They will provide a full date of birth (for the calculation of age), gender, and race/ethnicity.

Medical History

A verbal medical history that provides specific information regarding inclusion and exclusion (eligibility) criteria will be taken at screening including diagnoses and surgical procedures within the last 6 months.

Concomitant and Prohibited Medications

Investigator to review & document all current concomitant medications at day of screening and confirm eligibility per inclusion/exclusion criteria.

While enrolled in the study, participants should refrain from starting any anticoagulants, immunosuppressive therapies, oral steroids, or topical steroids applied near the area of the banded skin tag.

The use of a daily 81mg Aspirin is allowed, but note that this is a concomitant medication of interest and may increase bleeding and/or delay healing.

Modified Fitzpatrick Skin Type

Study team will administer to each participant who self-reports where their skin falls on the Fitzpatrick scale of burn versus tan with the ranking of I through VI.

SKIN	SKIN SKIN COLOR		REACTION	ACTION TO SUN	
TYPE			SUNBURN	TANNING	
ı		Light, pale white	Always burns	Never Tans	
II		White, fair	Usually burns	Tans with difficulty	
III	w	Medium, hite to olive	Sometimes mild burns	Gradually tans to olive	
IV		Beige olive, moderate brown	Rarely burns	Easy tan to moderate brown	
٧		Brown, dark brown	Very rarely burns	Tans very easily	
VI	la la	Very dark brown to black	Never burns	Always tans	

Image 5: Fitzpatrick Skin Type Chart

Limited Dermatological Exam

Investigator to examine potential skin tags to determine eligibility per inclusion criteria. Skin tag(s) will be measured and recorded. . No further dermatological exam to be performed.

Device Use and Band Application

The Investigator will complete training on device use for both automatic and manual options. Once a participant has met all inclusion and no exclusion criteria, the Investigator will apply the to the selected skin tag(s) and record location. Under protocol version 2, skin tags measuring between 4-6mm will all be banded using the micro size. The Investigator will place an adhesive bandage over each skin tag, following band application to prevent premature device detachment due to friction with clothing. Participants will receive a supply of bandages with their study kit, along with instructions for daily bandage removal and replacement for photo documentation. For those with two skin tags using the STR device, it is important to note which tag will be designated as #1 and which will be designated as #2 for eDiary reporting.

In the event of premature device detachment, the participant will note a detachment event in their daily eDiary. They will be instructed to contact the site to schedule a reapplication by the Investigator. The same device kit and application method (Auto or Manual) will be used for each rebanding. No more than two rebandings per skin tag will be permitted. The timing of rebanding, including the interval between band loss and reapplication, will be captured in the eDiary system. If a participant is unable to schedule a rebanding visit within 3 business days, they may be withdrawn from the study.

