Section 6.2.1	6.2.1 Stratification schematic to reflect 1:1 ratio of micro:standard STR device type	6.2.1 Stratification schematic to reflect 3:1 ratio of micro:standard STR device type	Due to micro and standard devices not reaching desired level of success in removing skin tags for 2-4 and 4-6 mm, respectively, the new recruitment efforts will focus on large skin tags and use of the micro device only
Section 4	Indications for use statement per device type	General indications for use statement to be determined upon completion of the study	Indications for use have been updated to be determined upon competition of the study
Section 6.2.1	80% compliance for eDiary completion to	participant payment of \$10 per eDiary completed	Participant compensation has been changed from overall compliance calculation to daily diary completion

			Tieaitii
	receive \$100 payment		to increase retention & eDiary completion through Day 20
Sections 6.2.3; 6.2.6	Rebanding not permitted; participants were withdrawn if device detached prematurely.	Participants may receive up to two rebanding visits per skin tag at the site in the event of premature device detachment. Rebanding details (e.g., timing, outcome) will be captured in the eDiary.	To allow controlled reapplication of the device and preserve participant data in cases of device failure, while maintaining consistency in study execution and analysis.
Section 6.2.3	No bandage was used after device placement.	A small adhesive bandage is applied at the screening visit to cover the banded skin tag. Participants receive approximately 20 bandages and instructions for replacement as needed.	To reduce risk of premature band detachment due to friction from clothing and improve retention of the device throughout the study period.
Section 6.2.1	No guidance on re- enrollment of prior participants	Participants previously enrolled may be re- enrolled if a different, previously unbanded skin tag is selected	To allow enrollment of individuals who meet inclusion criteria and had a device failure in a prior protocol version, without compromising data integrity
Sections 6.1, 14	The observed percentage of successful removal is 80%	The observed percentage of successful removal is 60%	Updated to reflect realistic expectations of effectiveness in a real-world setting.
Section 11.2	Not included	New section on withdrawal for non- compliance (e.g. missed rebanding)	Ensures clear criteria for withdrawal tied to study adherence.

TABLE OF CONTENTS

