11.2. Withdrawal Due to Participant Non-Compliance

A participant may be withdrawn from the study at the discretion of the Investigator and/ or Study Team in the event of non-compliance with the study protocol. In particular, if the study device detaches prematurely and the participant fails to contact the site or schedule a rebanding appointment, the participant may be withdrawn from the study. Failure to comply with rebanding procedures may render the participant ineligible to continue in the study.

All withdrawals and the reasons for withdrawal will be documented in the participant's source documentation and eCRF, as applicable.

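### Withdrawing a participant from the study when rebanding is not arranged can cut off outcome and safety data after a band failure, including data on a second tag that is still banded

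*Protocol*

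**What the plan says.** Section 6.2.3 sets out what follows early detachment. The participant records it in the daily eDiary and contacts the site, and up to two rebandings per tag are allowed. It then adds: "If a participant is unable to schedule a rebanding visit within 3 business days, they may be withdrawn from the study". It does not say when the three days start.

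Section 11.2 returns to the subject, leaves the decision to the Investigator and/or Study Team, gives no time limit, and says: "Failure to comply with rebanding procedures may render the participant ineligible to continue in the study". What must be kept at that point is limited: "All withdrawals and the reasons for withdrawal will be documented in the participant's source documentation and eCRF, as applicable". Neither section provides for diary, photo or visit follow-up after such a withdrawal.

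The unit of analysis is the tag. Under Section 6.1, "only a maximum of 2 tags per person will be treated", and "the number of tags for intention to treat (ITT) in each arm is 100 for a study total of 200 tags". Section 6.2.6.1 defines the efficacy report in the same terms: "The total number of skin tags treated and those successfully removed by use of the STR study device will be compiled and reported". The same section also describes data capture and archiving as per-protocol.

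The table of changes at the front of the protocol gives the reason for introducing rebanding in version 2: "To allow controlled reapplication of the device and preserve participant data in cases of device failure".

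**The concern.** Early band loss is a device failure in the protocol's own terms. A rule that can end participation after band loss, and not otherwise, selects on something close to the primary outcome. Participants whose bands stayed on never meet it.

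The rule also acts on the wrong unit. In a two-tag participant who loses one band, the other tag may still be banded and on course to fall off, yet withdrawal ends its follow-up as well.

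Two things are at stake. The first is removal by Day 20, which is confirmed at Visit 3 and judged against a 60% goal in each arm. The second is safety up to Visit 4. Neither the eDiary nor the two virtual visits needs a band in place, so losing a band is no reason in itself to stop collecting these data. Ending follow-up here works against the purpose that version 2 gives for rebanding.

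**Working it through.** The protocol gives no detachment or withdrawal rate, so there is no figure of its own to reproduce on this point. The counts of lost tags below are assumptions chosen to show a range.

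**Inputs.** Treated tags: 200 (Section 6.1). Goal: 60% of treated tags (Section 6.1). Visit windows: Visit 2 on Days 5-9, Visit 3 on Days 21-24, Visit 4 on Days 30-37 (Section 6.2.4). Assumed: 108 tags removed by the device, and 20 or 30 tags (10% or 15%) withdrawn.

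**1. All treated tags in the denominator.** 108/200 = 54.0%. If every lost tag is a failure, withdrawal does not change this.

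**2. Withdrawn tags dropped, all of them failures.** Rate = removed / (200 - lost).
- 20 lost: 108/180 = 60.0%
- 30 lost: 108/170 = 63.5%

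**3. Withdrawn tags dropped, half of them second tags.** Every withdrawn participant has two tags, one detached and not removed, the other removed with probability 54%.
- 20 lost (10 detached, 10 second tags): (108 - 10 × 0.54)/180 = 102.6/180 = 57.0%
- 30 lost (15 and 15): (108 - 15 × 0.54)/170 = 99.9/170 = 58.8%

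**4. Withdrawn tags kept and counted as not removed, without further follow-up.** In the setting of step 3, if none of the second tags' removals had been recorded before withdrawal:
- 20 lost: 102.6/200 = 51.3%
- 30 lost: 99.9/200 = 50.0%

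A denominator rule alone therefore prevents inflation, but it can misclassify second tags as failures. Only continued follow-up gives their true status.

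**5. Scale.** At 60% with 200 tags, the 95% half-width is 1.96 × √(0.6 × 0.4/200) = 6.8 points. (Section 6.1 gives 5.5%, which does not reproduce at 60%; that is a separate matter.) The shifts in steps 2 and 3 run from 57.0 - 54.0 = 3.0 to 63.5 - 54.0 = 9.5 points, so they can be as large as the sampling error.

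**6. Safety.** Section 9.2 defines prolonged healing as more than 14 days after the tag falls off or is removed by the Investigator. For a second tag that falls off on Day 12, that is after Day 12 + 14 = Day 26. Visit 4 is the only scheduled contact after that day. Section 9.3 ties serious adverse event reporting to the participant's final visit, so withdrawal shortens that period too.

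**The case against.** The strongest reply is that the loss is possible rather than certain. Both sections say that the participant may be withdrawn. Detachment alone does not trigger it, and the default is rebanding. Version 1 withdrew participants on detachment, so version 2 narrows the route. This stands. It would go too far to say that the rule defeats the amendment's purpose; it works against it.

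Second, the goal and the ITT label both refer to treated tags, and an analysis plan that is not shown may count withdrawn tags as not removed. This also stands, and on that reading there is no inflation. The per-protocol wording in Section 6.2.6.1 may point the other way, but it speaks of capturing and archiving data and does not define an analysis set. No counting rule recovers a second tag's true outcome or the safety data after withdrawal.

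A reader might also infer three stronger points that the protocol does not support:
- *That the rule carries a 54% device to the 60% goal.* This needs every lost tag to be a failure and the lost tags to leave the denominator. With second tags leaving as well, step 3 stays below 60%.
- *That adverse device effects after Visit 2 are lost.* Diary entries and photos up to withdrawal are kept. Only later events are at risk.
- *That any band lost on Days 10-20 meets no scheduled review within three business days.* At Visit 2 the task is explicit: "Study team to review any instances of premature band detachment, and to remind participant to schedule a rebanding visit if not already completed". The gap to Visit 3 is 12 to 19 days (21 - 9 to 24 - 5). But Visit 3 opens on Day 21 and reviews the diary, so a loss around Days 18-20 can fall within three business days of it, or earlier if a weekend intervenes. Daily diary entries, the reminder at Visit 1, the instruction to contact the site and the 24-hour number also operate between visits.

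**Conclusion.** The concern holds as a design weakness. Sections 6.2.3 and 11.2 permit withdrawal from the whole study on a trigger tied to device failure, applied to the person while outcomes are counted per tag, with no follow-up provided afterwards. Remaining diary, Visit 3 and Visit 4 data can be lost for the detached tag and for a second tag still banded, and analysis cannot restore them.

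The size is unknown. With 108 of 200 tags removed and 10% to 15% of tags assumed lost, the rate stays at 54% if all treated tags are counted and the lost ones are failures. If withdrawn tags are dropped, it reads 60.0% to 63.5% when all are failures, or about 57.0% to 58.8% when half are second tags. These figures rest on assumed withdrawal counts and on use of the discretion. The protocol does not establish that inflation will occur.

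**What to change.** In Sections 6.2.3 and 11.2, separate non-compliance with rebanding from withdrawal from follow-up. State that a participant for whom rebanding is not arranged continues the eDiary to Day 20 and Visits 3 and 4 for all treated tags, unless consent is withdrawn.

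State that every treated tag stays in the primary denominator, and that a tag with no documented removal by the device by Day 20 counts as not removed.

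Reconcile four places: the rationale in the table of changes, the ITT wording in Section 6.1, the per-protocol wording in Section 6.2.6.1, and the two withdrawal provisions, of which only one has a time limit. None of this requires a change to whether or when a tag is rebanded, and no such rule is proposed here.

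The cost is amendment wording and a few more diary payments. No visits are added, because Visits 3 and 4 are already planned for these participants. The reported removal rate may be lower.
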